	• Acceptability and tolerability of paediatric DE formulation; acceptability is defined as the overall ability and willingness of the patient to use the medicinal product as intended; tolerability is measured as premature treatment discontinuation, and adherence to trial medication.		
	The safety data will be evaluated based on the study observational period, i.e., from the index date (initiation of DE administration) onwards up until DE administration discontinuation $+ 3$ days of REP or switch to other anticoagulation therapy $+ 3$ days or planned end of 6-month observation time whichever occurs earlier.		
	Patients who continued secondary VTE prevention after acute VTE treatment will conduct two follow up visits: at the end of DE treatment for acute VTE, at discontinuation of DE for secondary VTE prevention or after total 6 months of DE administration, whatever occurs first.		
	All data will be obtained by qualified clinicians according to the standard medical practice.		

1160.307 PASS NIS Protocol

Data sources:	Newly collected data and/or data collected from medical records will be entered by the site directly in an electronic data capture (EDC) system via an Internet portal. All sites will be fully trained for using the EDC system and BI AE/SAE reporting procedure. It is the Principal Investigator's responsibility to ensure for his/her site the accuracy of the data provided to the program by any site staff that is trained for the program data collection.
Study size:	The study sample size is based on the anticipated usage of DE for VTE treatment and prevention. An overall 50 patients under 2 years of age will be enrolled in the study. Approximately 30 paediatric study sites with experience in VTE anticoagulation treatment and prevention will be selected for the PASS in EU/EEA states. Approximately 10 EU/EEA countries are planned to engage in this study.

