8.1 STUDY DESIGN

The DE Post-Authorization Safety Study (PASS) for VTE treatment and prevention of recurrent VTE in children under 2 years of age is designed as a prospective, non-interventional European multinational multi-centre, single-arm cohort study based on newly collected data of patients anticoagulated by DE for acute VTE treatment or prevention of recurrent VTE.

The study is designed to collect and evaluate DE safety in the context of routine anticoagulation care provided in the EU/EEA for children under 2 years of age. The duration of the study will be up to 2 years with the goal to enrol 50 evaluable patients under DE administration. Approximately 10 EU/EEA countries are planned to engage in this study.

The study will be conducted in paediatric hospitals or paediatric departments of *European Economic Area* member states where VTE patients of the evaluated age group are treated, depending on country regulations and requirements.

In order to assure assessment of representativeness of the PASS, all patients under 2 years who required anticoagulation and sign informed consent will be screened for potential participation in the study. Screening details will be entered in the Screening Log, which will contain final conclusion on study eligibility with clarification of screening failure if not enrolled in the PASS. If a patient completes all study entry criteria, a baseline part of the Screening / Baseline visit will be conducted, and the patient will enter an observational study period.

During the observational period safety outcomes, which comprise all specific clinical safety data connected with anticoagulation management of the children under 2 years of age, will be collected.

The study observational period is defined as a time period from the index date (i.e., initiation of DE administration) onwards up until DE administration discontinuation + 3 days of Residual Effect Period (REP) or switch to other anticoagulation therapy + 3 days of REP or planned end of 6 month observation time, whatever occurs earlier. Overall duration of the study observational period for any

patient will not exceed 6-month period of anticoagulation. Patients will not be followed outside the observational period.

Duration of the observational period will be as follows:

- up to 3 months from the day of DE initiation defined as index date for the treatment of acute VTE and
- up to 6 months from index date for prevention of recurrent VTE.

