Patients after completion of acute VTE treatment may continue anticoagulation due to unresolved VTE risk factors. The duration of the VTE treatment and secondary VTE prevention periods will be based on investigator judgement. Total duration of the observational period for this group will be performed until DE administration discontinuation + 3 days of REP or planned end of 6-month observation time, whatever occurs earlier.

Patient who completed acute VTE treatment and continued DE anticoagulation due to unresolved VTE risk factors will be considered as one unique patient. However, safety outcomes of each anticoagulation period will be evaluated within the corresponding cohort.

Anticoagulation of more than 6-month duration, if required due to the presence of unresolved VTE risk factors, will not be covered in this study setting.

The duration of anticoagulation outlined in this PASS study is in accordance with international guidelines for management of VTE paediatric patients [P19-00949], results and experience of the previous DE registrational studies, and reflect routine VTE paediatric care. The recommended duration of anticoagulation treatment is up to 3 months for children above one year of age. For neonates and infants (children under 1 year), the usual recommended treatment duration is 6 weeks. However, it may be extended, if the VTE clinical risk factors are unresolved at the end of the 6-week treatment period. Recommendations on the duration of anticoagulation for prevention of VTE recurrence depend on the presence of unresolved VTE clinical risk factors and may continue for an indefinite period of time. Final decision on the duration of VTE treatment and /or secondary prevention periods will be based on investigator's judgment.

Safety data collection will be conducted at Screening/Baseline and Follow up visits for both VTE treatment and prevention of recurrent VTE groups. Visit details provided in the Section 8.2.3. "Study visits".

The study is observational and does not entail any change in prescribing pattern or management policies which are left to the discretion of the treating physician. No special evaluation procedure is required.

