8.3 VARIABLES

8.3.1 Exposures

As per inclusion criteria, all patients in this single arm study will receive DE and will be evaluated as such unless there is no documentation of DE administration as per CRF.

Dabigatran exposure is defined as from start of DE administration (index date) up to the DE administration discontinuation + 3 days of REP or switch to other anticoagulation therapy + 3 days of REP or planned end of observation time whichever occurs earlier.

Dabigatran exposure for the VTE treatment group planned up to a 3-month period and for the prevention of recurrent VTE group up to 6 months (see Section 8.1 "Study design").

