8.3.2.3 Further outcome

• To assess acceptability and tolerability of paediatric formulation.

Acceptability is defined as the overall ability and willingness of the patient and/or parent (legal guardian) to use the medicinal product as intended.

Tolerability is measured as premature treatment discontinuation, treatment interruption, and adherence to trial medication.

Assessment of acceptability and tolerability.

The overall clinical assessment of acceptability and tolerability will be performed by the parent / legal guardian and investigators by completing a standardized questionnaire. In between baseline and study final visits, the parent /legal guardian will be asked to document any failed or missed intake of medication (e.g., the patient did not swallow the medication, or doses missed, etc.) and provide this documentation to the investigator. The parent / legal guardian will be instructed to inform the

1160.307 PASS NIS Protocol

Proprietary confidential information © 2024 Boehringer Ingelheim International GmbH or one or more of its affiliated companies

investigator immediately if two or more consecutive doses of study medication are missed or not taken correctly.

Assessment of the representativeness of the study cohort.

Screening Log with details of all patients requiring anticoagulation due to acute VTE treatment and/or secondary VTE prevention will be used for assessment of the representativeness of the study cohort, when all required anticoagulation patients will be compared with patients enrolled in the PASS.

All parents/legal guardians will be asked to sign informed consent before the screening procedures. Screening Log will contain demography, details of conditions that require anticoagulation, conclusion on entry in the PASS or comments on reasons for screening failure.

The safety outcomes will be evaluated based on the on-treatment period, i.e., from start of DE administration (index date) up to DE administration discontinuation + 3 days of REP or switch to other anticoagulation therapy + 3 days of REP or planned end of observation time, whatever occurs earlier.

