8.7.1 Main analysis

As this is a descriptive non-interventional, single-arm study, no hypotheses will be tested, rather all variables will be presented in summary using descriptive statistics (absolute and relative frequencies, means, standard deviations, medians, ranges, minimum and maximum values, 95% confidence intervals [CI] and incidences as appropriate for the nature of the variables (i.e., categorical, or continuous))

Safety outcomes will be summarized as incidence with 95% CIs (using Wilson method). All AE/ verbatim terms will be recorded and coded using the Medical Dictionary for Regulatory Activities (MedDRA). Analysis of AEs and other outcomes will be based on treatment emergent events and on all patients, who were treated with dabigatran at least once. Treatment-emergent events are defined as events occurring from start of DE administration (index date) up to DE administration discontinuation + 3 days of Residual Effect Period (REP) or switch to other anticoagulation therapy or planned end of observation time, whatever occurs earlier.

Concomitant medications will be coded according to the World Health Organisation Drug Dictionary (WHO-DD).

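### Section 8.7.1 stops counting events on the day of a switch to another anticoagulant, while the abstract and Sections 8.1, 8.3.1 and 8.3.2.3 count the 3 days after it

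*Protocol*

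**What the plan says.** The primary outcome is the incidence of any bleeding, major or non-major (Section 8.3.2.1). Section 8.7.1 reports safety outcomes as incidence with Wilson 95% intervals. It bases adverse events and other outcomes on treatment-emergent events in all children treated at least once.

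The event window is written out several times:

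- **Section 8.7.1:** discontinuation plus 3 days of "Residual Effect Period (REP) or switch to other anticoagulation therapy or planned end of observation time, whatever occurs earlier". The 3 days attach to discontinuation only.
- **Section 8.1** (observational period): "switch to other anticoagulation therapy + 3 days of REP or planned end of 6 month observation time, whatever occurs earlier".
- **Section 8.3.1** (exposure): "switch to other anticoagulation therapy + 3 days of REP or planned end of observation time whichever occurs earlier".
- **Section 8.3.2.3** (the on-treatment period on which safety outcomes are to be evaluated): "switch to other anticoagulation therapy + 3 days of REP or planned end of observation time, whatever occurs earlier".
- **Abstract** (study design and variables): 3 days after the switch in both places.
- **Sections 8.1 and 8.2.3, children who go from acute treatment to prevention:** "DE administration discontinuation + 3 days of REP or planned end of 6-month observation time, whatever occurs earlier". A switch is not mentioned.

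Section 8.1 also sets the length of observation by cohort. For acute VTE it is "up to 3 months from the day of DE initiation defined as index date for the treatment of acute VTE", and for prevention of recurrence it is up to 6 months.

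**The concern.** The window decides whether a bleed enters the numerator of the primary outcome, and the analysis section sets it differently from the sections that define exposure and outcomes. The protocol uses a 3-day residual period because it treats the drug's effect as lasting that long after the last dose. That reasoning is the same whether a child stops or changes to another anticoagulant. Section 8.7.1 applies it only to the child who stops.

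The events at stake would be recorded and then left out, because the observational period in Section 8.1 includes those days. The difference also has a fixed direction, since the shorter window lies inside the longer one.

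Timing matters too. Section 8.7 requires the SEAP to be final only before the end of data collection. In an open, single-arm study the choice between the two rules could therefore be made when bleed and switch dates can already be seen.

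**Working it through.** The protocol gives no expected bleeding rate, so there is no figure of its own to reproduce. The check is a comparison of texts followed by an illustration of size. Event days and event counts below are assumptions. The target of 50 comes from Section 8.5 and the Wilson method from Section 8.7.1.

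**1. The switch rule applied to one child.** Index day 0, switch on day 30, first bleed on day 32.

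| Rule | Window ends | Bleed on day 32 |
|---|---|---|
| Section 8.7.1 | day 30 | not counted |
| Abstract, Sections 8.1, 8.3.1, 8.3.2.3 | 30 + 3 = day 33 | counted |

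Treating the switch as a form of discontinuation does not remove the conflict. Discontinuation plus 3 days would give day 33, but Section 8.7.1 takes the earliest of its listed ends, and the bare switch date (day 30) comes first.

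**2. Direction.** For every child who switches, the 8.7.1 window is contained in the other. Its bleeding count is therefore equal or lower, never higher.

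**3. Size per child.** With p = x/n and z = 1.96, the Wilson limits are

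[p + z²/(2n) ± z·√(p(1−p)/n + z²/(4n²))] / (1 + z²/n).

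For n = 50, z²/n = 3.8415/50 = 0.0768.

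- x = 0: the upper limit is 0.0768/1.0768 = 7.1%.
- x = 1: the centre is (0.02 + 0.0384)/1.0768 = 0.0542 and the half-width is 1.96·√(0.000392 + 0.000384)/1.0768 = 0.0507, giving 0.4% to 10.5%.

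| Bleed excluded | Bleed included |
|---|---|
| 0/50 = 0% (0 to 7.1%) | 1/50 = 2% (0.4 to 10.5%) |
| 5/50 = 10% (4.3 to 21.4%) | 6/50 = 12% (5.6 to 23.8%) |
| 10/50 = 20% (11.2 to 33.0%) | 11/50 = 22% (12.8 to 35.2%) |

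The shift is 1/50 = 2 percentage points per child whose only bleed falls in the 3 days. Within either cohort it is 1/n, which is larger for n below 50. The split between cohorts is not given.

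**4. Share of the window.** Three days are 3/(42 + 3) = 6.7% of a 6-week course plus residual period, and 3/(91 + 3) = 3.2% of a 3-month course plus residual period.

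**5. Residual days after a full acute course.** Take 3 months as 91 days. A child treated for acute VTE stops on day 91 and bleeds on day 93. Under discontinuation plus 3 days the window runs to day 94 and the bleed counts. Under a strict limit of 3 months from the start of dabigatran it ends on day 91 and the bleed does not count. No section says which applies. Sections 8.3.1, 8.3.2.3 and 8.7.1 refer only to the planned end of observation, without a number.

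**The case against.** **It is a single phrase, and the detail belongs in the SEAP.** Four parts of the protocol agree, and Section 8.7 calls itself a summary. It is also true that no event goes unrecorded, because adverse events are collected from consent to the end of the study (Section 10.2). This makes the repair easy but does not settle which rule applies. Sections 8.3.2.3 and 8.7.1 both say on which window outcomes are evaluated, and a SEAP cannot follow both.

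**The effect may be small.** This stands. The window is 3 days, the number of switchers is unknown, and no hypothesis is tested. At 10 or 11 bleeds in 50 the two intervals largely overlap. The contrast is sharpest for rare events such as major bleeds, where it can separate none observed from one observed.

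**Three stronger readings are tempting, and the protocol does not support them.**

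- A reader might infer that bleeding prompts switching, so the lost days are where bleeds cluster. But a bleed that prompts a switch starts before it and counts under both rules. Only bleeds that start afterwards are affected.
- A reader might infer that time at risk is distorted as well. The protocol states incidence with Wilson intervals, which is a proportion, and gives no person-time rate. Only the numerator is in question.
- A reader might infer that the acute cohort has two conflicting caps, 3 months and 6 months. The abstract and Sections 8.1, 8.2.2 and 8.3.1 consistently give acute VTE up to 3 months. Six months is the overall maximum, the prevention limit, and the limit for children who move from acute treatment to prevention. The later bleeds of that last group are counted in the prevention cohort. What remains open is the narrow matter of the residual days in step 5.

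**Conclusion.** The inconsistency is real and concerns the primary outcome: Section 8.7.1 ends the window at the switch, and the abstract and Sections 8.1, 8.3.1 and 8.3.2.3 end it 3 days later. The analysis-section rule can only lower the bleeding count or leave it unchanged, and it treats children who switch differently from those who stop.

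The size is 2 percentage points per affected child at the planned 50. This assumes that 50 children are analysed and that the child has no other counted bleed. The total cannot be estimated, because the protocol gives neither the number of switchers nor a bleeding rate.

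The treatment of the residual days after a full 3-month acute course is a secondary point that needs clarification. It is not a second contradiction.

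**What to change.** 1. Define the event window once and refer to that definition in the abstract and in Sections 8.1, 8.2.3, 8.3.1, 8.3.2.3 and 8.7.1. Say there that it also governs a switch by a child who has gone from acute treatment to prevention.
2. In Section 8.7.1, add the 3 days of residual effect period after the switch, as the other sections have it.
3. Flag events in those 3 days as occurring on another anticoagulant, so that a reader can see the result with and without them.
4. State whether the 3 residual days after a full 3-month acute course fall inside the acute cohort's observation window. Do not extend that cohort's window to 6 months, which would contradict Sections 8.1, 8.2.2 and 8.3.1.

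The change concerns which events are counted, not treatment. Its cost is wording in the protocol and SEAP, plus the review that Section 9.1 requires for amendments. The switch correction needs no new data, because the post-switch days already lie inside the observational period of Section 8.1. It should be settled before the SEAP is final.

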8.7.2 Further analysis

To assess the representativeness of the study cohort, the screening log will be summarized for screening failures and eligible patients who enter the study.

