However, limited evidence is available in early age children (from birth to < 2 years) for treatment of VTE and prevention of recurrent VTE. This age group also demonstrate the most marked differences from adults in hemostaseology [R15-4967]. The results of acute VTE treatment in this age group were evaluated in 35 cases of the DIVERSITY study, where 22

1160.307 PASS NIS Protocol c3592 Proprietary confidential information © 2024 Boehringer Ingelheim International GmbH or one or more of its affiliated companies

patients received DE and 13 received SOC [P20-07911]. The long-term secondary VTE prevention study evaluated 9 children in this early age group [c29754273-01]. The limited number of neonates and infants evaluated in the DE paediatric program was connected with multiple challenges, including the relatively rare condition, a critically ill population with life-threatening comorbidities, use of aggressive treatments, limited blood volumes that can be drawn for study purposes and, finally, parental consent that is often difficult to obtain in young children with acute serious conditions [R11-4524, P17-11774, P19-00949, R20-3318]. Thus, post-authorization data collection is planned to characterize the safety profile of dabigatran in children under 2 years of age. The aim of this PASS is to evaluate the safety of all paediatric patients under 2 years of age receiving DE in a routine clinical practice setting.

7. **RESEARCH QUESTION AND OBJECTIVES**

The objective of this study is to evaluate the safety of DE for VTE treatment and prevention of VTE recurrency in children from birth to < 2 years of age in a routine clinical practice setting.

Primary objective:

• To estimate the incidence of any bleeding event defined as Major Bleeding Event (MBE) or Non- Major Bleeding Event (Non-MBE) among the children under 2 years of age on DE administration.

Secondary objective:

- To estimate the incidence of AEs.
- To estimate the incidence of SAEs.

Further objective:

• To assess acceptability and tolerability of paediatric formulation.

8. **RESEARCH METHODS**

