8.2.2 Study population

Paediatric patients from birth to < 2 years of age considered by investigator after screening as eligible for DE treatment of acute VTE or secondary prevention of recurrent VTE will be enrolled in the PASS and evaluated for up to 3 months in case of acute VTE treatment, and up to 6 months in case of prevention of recurrent VTE.

Patients after completion of acute VTE treatment may continue anticoagulation as secondary VTE prevention due to unresolved VTE risk factors in accordance with investigator's judgment. Total observational period for this group, which include VTE treatment and prevention will be also up to 6 months duration. Further anticoagulation, if required due to unresolved VTE risk factors, will be continued outside the study setting.

Inclusion criteria:

- Written informed consent from parents/care givers,
- Children from birth to less than 2 years of age,
- Initiation of DE administration:
 - for treatment of VTE or/and
 - prevention of recurrent VTE due to presence of unresolved clinical VTE risk factor(s).

Exclusion criteria:

1160.307 PASS NIS Protocol

- Participation in any Randomised Clinical Trial or use of any investigational product,
- Any contraindications to DE according to the EU SmPC.

Paediatric population will be stratified into two groups according to the EU DE SmPC:

- children anticoagulated with dabigatran due to acute VTE treatment
- children anticoagulated with dabigatran for prevention of recurrent VTE due to the presence of an unresolved VTE clinical risk factor.

Patients who completed acute VTE treatment and continued DE anticoagulation due to unresolved VTE risk factors will be considered as one unique patient. However, safety outcomes of each anticoagulation period will be evaluated within the corresponding cohort.

The target sample size for the study is considered to be 50 evaluable patients enrolled from approx. 30 paediatric sites over an approximate 1.5-year period with a total approximate 2-year study duration.

The enrolment period is planned from Q4 2022 (FPI) to the Q2 2024 (LPI) depending on the availability of DE paediatric formulation (granules) on the market.

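### The only representativeness check compares children started on DE with a log in which not starting DE is itself a reason for failure, so it mainly describes selection to DE; the log population is also defined in two ways

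*Protocol*

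**What the plan says.** **Target.** Section 6 gives the aim as to "evaluate the safety of all paediatric patients under 2 years of age receiving DE in a routine clinical practice setting".

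**Who is logged.** Section 8.1, repeated in Section 8.2.3, says that "all patients under 2 years who required anticoagulation and sign informed consent will be screened for potential participation in the study", and gives assessment of representativeness as the reason. The Abstract likewise refers to an indication for anticoagulation without limiting it to VTE. Section 8.3.2.3 is narrower and describes a "Screening Log with details of all patients requiring anticoagulation due to acute VTE treatment and/or secondary VTE prevention".

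**What is compared.** Section 8.3.2.3 says the log serves this purpose "when all required anticoagulation patients will be compared with patients enrolled in the PASS". Section 8.7.2 carries it out: "the screening log will be summarized for screening failures and eligible patients who enter the study".

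**Who can enter.** Section 8.2.2 requires "Initiation of DE administration" for VTE treatment or prevention of recurrence. It excludes "Participation in any Randomised Clinical Trial or use of any investigational product" and any contraindication to DE.

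**What the log holds.** Sections 8.2.3 and 8.3.2.3 list demography, the condition needing anticoagulation, the eligibility conclusion and comments on failure. The anticoagulant started is not listed. Consent is sought before screening.

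**The concern.** Representativeness of a single-arm DE cohort is naturally judged against the DE users it is meant to describe. Here the comparator is the anticoagulated population in general, and the criterion that separates it from the cohort is the treatment itself.

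A difference between the two groups could be read as an unrepresentative DE sample when it only shows that sites give DE to different children. Similarity could be read as reassurance although no comparison with non-enrolled DE users was made. With a target of 50 patients, no comparator arm and a population that Section 8.9 calls heterogeneous, this is the only stated check on representativeness. What is at stake is the wording of the generalisability statement.

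**Working it through.** The protocol states no number screened, failure rate or DE uptake, so there is no figure to reproduce. The main check is logical, with an illustration on assumed inputs.

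**Step 1: who can be a screening failure.** Apply Section 8.2.2 to a consented child under 2 in the log.

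- Not started on DE: always a failure.
- No VTE indication: a failure, possible only under the wider log definition. A few such children may have received DE.
- Already on DE and not initiating it: can be a failure, and is a DE user.
- In a randomised trial or using an investigational product: a failure, and may be a DE user.
- Contraindication to DE: a failure, and a DE user only if DE was given regardless.

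All non-DE children fall on the failure side, and DE children reach it only by exceptions. Comparing the enrolled with the whole log, as Section 8.3.2.3 words it, does not change this. The log is the enrolled plus the failures, so any difference comes from the failures.

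**Step 2: how large the non-DE share could be.** Let u be the share of logged children given DE and e the share of those who still fail entry. Both are assumptions.

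Non-DE share of failures = (1 − u) / [(1 − u) + u × e]

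| u | e = 2% | e = 20% |
|---|---|---|
| 10% | 99.8% | 97.8% |
| 30% | 99.2% | 92.1% |
| 50% | 98.0% | 83.3% |
| 80% | 92.6% | 55.6% |

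For example, u = 0.80 and e = 0.20 give 0.20 / (0.20 + 0.16) = 0.556. At the other end, u = 0.10 and e = 0.02 give 0.90 / 0.902 = 0.998.

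**Step 3: how many DE-treated failures the log would hold.** The number screened to enrol 50 is 50 / [u × (1 − e)]. With u = 0.20 and e = 0.05 this is 50 / 0.19 = 263, so 213 fail. DE-treated failures are 263 × 0.20 × 0.05 = 2.6.

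**Step 4: DE users who never reach the log.** If a share r of DE families refuse consent and there are no other losses, the number absent is 50 / (1 − r) − 50. That is about 6 at r = 10%, 21 at 30% and 50 at 50% (r is assumed). Under most of these assumptions, refusers outnumber the DE-treated failures in Step 3.

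**Step 5: the two log definitions.** Under Sections 8.1 and 8.2.3, a child anticoagulated for a non-VTE reason is logged and fails. Under Section 8.3.2.3 that child is not logged. The two versions give different failure groups and different tables.

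**The case against.** The strongest case on the other side has four parts.

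- **A different reference population.** Section 8.3.2.3 says openly that the comparison is with all anticoagulated patients, and Section 8.9 voices concern about comparability with other VTE populations. Comparing DE children with other anticoagulated children does inform that. This stands, and the comparison is worth keeping. It does not answer the question set by the aim in Section 6, and the protocol labels it representativeness of the study cohort.
- **Failures can already be separated.** Comments on failure are logged, Section 8.7.2 does not require pooling, and Section 8.7 leaves detail to an analysis plan that is not shown. This stands in part. Free comments are not a structured record of the drug started, and an analysis plan cannot supply a field that was not collected. The protocol itself fixes the log population and the comparison.
- **Uptake may be high.** Section 8.2.1 says sites with DE available for children will be sought. This stands. Section 8.9 says recruitment depends strongly on market uptake and availability, so high uptake cannot be presumed either.
- **The stakes are modest.** The analysis is descriptive, tests nothing and triggers no decision. This stands.

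A reader might also infer that enrolled children should be compared with logged children who received DE but were not enrolled. The documents do not support that remedy. Because consent comes before the log, this group is a handful of children mostly excluded by design, so it says little about eligible DE users in routine care.

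**Conclusion.** The point holds. As defined, the check mainly describes selection to DE and, under the wider log definition, VTE versus other indications. It cannot show whether the cohort represents children under 2 receiving DE. The two definitions of the log population contradict each other and need reconciling in any case.

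The size is uncertain. Non-DE children are about 56% to over 99% of screening failures for assumed uptake of 10% to 80%, with 2% to 20% of DE children failing entry. They remain the majority throughout that range.

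Two stronger readings are tempting but not supported. One is that nearly all failures did not receive DE. That follows at low or moderate uptake (92% or more for u up to 30%) but not at high uptake, and the protocol gives no uptake figure. The other is that the generalisability conclusion would be wrong whichever way the table came out. For a descriptive summary with no decision rule, uninformative or open to misreading is as far as the text goes.

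**What to change.** 1. Use the Section 8.3.2.3 definition (acute VTE treatment and/or secondary prevention) in the Abstract and Sections 8.1 and 8.2.3.
2. Add one log field: anticoagulant started (DE / other / none).
3. In Section 8.7.2, tabulate enrolled children against screening failures split by anticoagulant and failure reason, not pooled.
4. Label the comparison with VTE children on other anticoagulants as a description of who is selected for DE. Do not rest the representativeness statement on logged children who received DE but were not enrolled.
5. State that the log cannot show representativeness with respect to DE users whose parents refuse consent. Alternatively, where local rules allow, report an anonymous count per site of all children under 2 starting DE.

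**Cost.** One extra field, one split table, aligned wording and a more modest statement on representativeness. Version 3.0 is dated January 2024 and enrolment was planned from Q4 2022, so the field may have to be completed retrospectively for children already logged. The bleeding, AE and SAE incidences do not change.
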